2. INTRODUCTION

2.1. Background

Pulmonary arterial hypertension (PAH) is a severe, incurable disease characterized by remodeling of the pulmonary arterial bed, leading to elevations in resting mean pulmonary artery pressures, subsequent right ventricular hypertrophy, and eventually, right heart failure and (Agarwal & Gomberg-Maitland, 2011). Current standard-of-care therapies for PAH target 3 different pathways – namely, the endothelin-1 pathway, the nitric oxide pathway, and the prostacyclin pathway – and act primarily as vasodilators. They reduce PAH symptoms and may slow disease progression, but they lack compelling disease-modifying properties.

Protocol RVT-1201-2002

Effective: 19JAN2022

Several lines of evidence implicate serotonin (5-hydroxytryptamine [5-HT]) in the pathophysiology of PAH where there are findings that 5-HT plasma levels are markedly elevated in PAH (Humbert et al., 2002); tryptophan hydroxylase (TPH) 1, the key rate-limiting enzyme in the biosynthesis of systemic 5-HT, is overexpressed in lung tissue of PAH patients (Eddahibi, 2006), and 5-HT acts on pulmonary artery smooth muscle cells to induce vasoconstriction and proliferation (MacLean & Dempsie, 2010). In addition, 5-HT acts at the 5-HT1B receptor and the 5-HT transporter to mediate constriction and proliferation of pulmonary artery smooth muscle cells (MacLean & Dempsie, 2010). Finally, genetic deletion and pharmacological inhibition of TPH1 protects against the development of experimentally induced PAH (Abid et al., 2012; Izikki et al., 2007) in nonclinical pharmacology models. In aggregate, these findings indicate that modulation of the 5-HT pathway by TPH1 inhibition is a novel approach that differentiates itself mechanistically from current therapeutic options and offers the potential to modify the underlying disease pathophysiology and progression of PAH (Aiello et al., 2016; MacLean, 2018).

A therapeutic strategy is needed to safely and effectively inhibit TPH1 activity in peripheral tissues, without unwanted central nervous system (CNS) effects that result from inhibition of TPH2, the predominant TPH isoform in the CNS.

Rodatristat ethyl is a peripherally restricted TPH1/TPH2 inhibitor with little CNS penetration. Nonclinical data indicate that neither rodatristat ethyl nor rodatristat cross the blood brain barrier to a pharmacologically relevant level and do not lower brain levels of 5-HT in nonclinical pharmacodynamic studies in rats. By limiting inhibition to TPH1 in the periphery, rodatristat ethyl may avoid potential untoward CNS effects that could otherwise be a consequence of inhibiting TPH2-mediated CNS 5-HT production (Kim et al., 2015; Shi et al., 2008).

Rodatristat ethyl is a prodrug that is rapidly hydrolyzed to rodatristat, a potent TPH inhibitor that reduces peripheral 5-HT levels in the gut mucosa, lung, and serum in animal models of PAH. In vitro, nonclinical, and human pharmacokinetic (PK) studies to date have provided valuable information on the PK properties of rodatristat ethyl and its active moiety, rodatristat. Rodatristat ethyl has low to moderate oral bioavailability in nonclinical species and is rapidly converted to rodatristat in vivo. Both rodatristat ethyl and rodatristat are highly protein bound and little is excreted in the urine. Biliary excretion predominates in rats and no further metabolism of rodatristat has been detected in human hepatocyte preparations. However, preliminary investigations have also identified a metabolite, M15, in the plasma of dogs and humans after

administration of rodatristat ethyl. After single-dose administration, the half-life of rodatristat ethyl and rodatristat are approximately 5 and 12 hours, respectively, reaching steady-state exposure, according to trough concentrations, by Day 5. The highest exposures achieved in healthy subjects to date were reached on Day 7 following 800 mg twice daily (BID) doses of rodatristat ethyl.

Protocol RVT-1201-2002

Effective: 19JAN2022

Rodatristat ethyl was selected for development in the treatment of PAH based on a range of criteria, including achieving efficacy endpoints in nonclinical in vivo models of PAH, pharmacokinetic (PK) parameters, and biomarker endpoints related to both changes in systemic 5-HT levels and PAH pathology.

Reductions in biomarkers indicative of decreased 5-HT biosynthesis were observed in healthy subjects receiving repeat twice daily (BID) oral doses (range 100 to 800 mg BID) of rodatristat ethyl over 14 days. Rodatristat ethyl doses of either 400 or 800 mg BID achieved reductions in 5-HT by Day 14 comparable to those associated with efficacy in the rodent models of PAH.

2.2. Study Rationale

Rodatristat ethyl is expected to have efficacy for PAH. Results from nonclinical pharmacology studies demonstrate that rodatristat ethyl is a potent and selective inhibitor of TPH1 with the potential to ameliorate disease by halting or reversing the pulmonary vascular remodeling characteristically observed. Through inhibition of TPH1, rodatristat ethyl is expected to improve cardiopulmonary hemodynamics, functional capacity, PAH symptoms, and right ventricular (RV) function via its novel antiproliferative and anti-remodeling mechanism of action.

This study will evaluate rodatristat ethyl doses of 300 mg BID and 600 mg BID. Dose selection was guided by the goal of demonstrating a dose/exposure efficacy relationship and was supported by nonclinical pharmacology, toxicology, and animal model efficacy data. Results from Phase 1 human studies suggest that these dosing regimens should be safe and generally well tolerated with dose-proportional differences in systemic drug exposure. Further details regarding the dose rationale can be found in Section 4.7.

2.3. Benefit/Risk Assessment

Summaries of findings from both clinical and nonclinical studies conducted with rodatristat ethyl as well as more detailed information about the known and expected benefits and risks and reasonably expected adverse events (AEs) of rodatristat ethyl may be found in the Investigator's Brochure. This section outlines the potential adverse events of special interest (AESI; based either on preclinical or clinical data generated to date, the mechanism of action of rodatristat ethyl, or the prescribing information for telotristat ethyl [a TPH inhibitor previously approved for the treatment of carcinoid syndrome-related diarrhea] and mitigation strategies for this protocol. The potential risk for QTc prolongation (described in the Investigator's Brochure) will be further evaluated in a definitive thorough QT study in the future. Until further data are available in that regard, cardiac arrhythmia, related to an increase in QT/QTc interval, will be treated as a potential AESI and has therefore also been included in the table of potential risks below.

Although any potential benefits to patients with PAH will not be known until the study is completed, the development of a drug with disease-modifying potential will certainly be of value to patients with this diagnosis.

Potential Risk	Mitigation Stra	itegy
	Impact on Eligibility	Monitoring and Stopping Criteria OR Management Criteria
Severe constipation	None	Severe constipation (e.g., obstipation with manual evacuation indicated) and/or severe, persistent, or worsening abdominal pain would warrant withdrawal from the study.
Depression/other mood-related disturbance due to central depletion	 Exclusion of patients with active suicidal thinking or behavior at Screening/Baseline based on the Columbia-Suicide Severity Rating Scale (C-SSRS) Exclusion of patients with severe depression at Screening/Baseline based on the Quick Inventory of Depressive Symptoms Clinician-Rated (QIDS-C) or the Hospital Anxiety and Depression Scale (HADS) 	 Withdrawal of patients with: Any significant worsening on postdose C-SSRS indicative of active suicidal ideation with intent to act or suicidal behavior Severe depression or anxiety based on a HADS Depression or Anxiety Score ≥ 15 or a QIDS-C Total Score ≥ 16. Any severe psychiatric or CNS AE as determined by the Investigator.

Protocol RVT-1201-2002 Effective: 19JAN2022

Potential Risk	Mitigation Stra	ntegy
	Impact on Eligibility	Monitoring and Stopping Criteria OR Management Criteria
Hepatic enzyme elevations	Exclude patients with alanine aminotransferase (ALT) / aspartate aminotransferase (AST) / gamma-glutamyl transferase (GGT) results greater than 2X upper limit of normal (ULN) and/or TBL > 2X ULN	Withdrawal criteria for abnormal liver function tests set at: • ALT or AST > 3X ULN and TBL > 2X ULN (or international normalized ratio (INR) > 1.5) • ALT or AST > 3X ULN with appearance of fatigue, nausea, vomiting, right upper quadrant pain or tenderness, fever, rash and/or eosinophilia (> 5%) • ALT or AST > 5X ULN for > 2 weeks • ALT or AST > 8X ULN
Cardiac arrhythmia, related to an increase in QT/QTc interval	 Exclude patients with: QTcF > 450 ms (males) or > 470 ms (females) Known congenital Long QT Syndrome (LQTS), or known family history of LQTS Clinically significant electrolyte abnormality (i.e., hypokalemia, hypocalcemia, hypomagnesemia) Concomitant use of QT-prolonging drugs clearly associated with a risk of Torsades de Pointe (see Appendix 1) 	Withdrawal criteria for abnormal/worsening QT interval prolongation: • QTcF interval > 500 ms • QTcF interval > 480 ms AND increase from baseline ≥ 60 ms • QTcF interval > 480 ms associated with syncope, life-threatening arrhythmias, resuscitated cardiac arrest, or seizure

ciences GmbH Effective: 19JAN2022

Protocol RVT-1201-2002

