4.4.1.2. Aminotransferase (Alanine aminotransferase or Aspartate Aminotransferase) Elevation

Management recommendations for ALT or AST elevations are based on U.S. Food and Drug Administration (FDA) Guidance for Liver Toxicity.

In general, all baseline or treatment-emergent ALT or AST elevations > 3X ULN should be confirmed within 48 to 72 hours with repeat assessments of ALT and AST as well as TBL, alkaline phosphatase (ALP), prothrombin time/INR, and complete blood count for eosinophil levels. Further details for managing IP reduction, restart, and discontinuation can be found in Appendix 3.

If at any time, the criteria as outlined in Section 8 are met, the IP must be permanently discontinued.

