7.12. Criteria for Investigational Product/Study Termination

All criteria for IP and study termination are the same as in the Main Study and can be found in Section 8.

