8.1. Discontinuation of Investigational Product

The Medical Monitor should be notified of any change to background PAH therapy to determine any need for withdrawal. See Section 8.2 for study withdrawal procedures.

Patients meeting any of the following liver chemistry criteria must be withdrawn (IP should be discontinued immediately) from the study by the Investigator:

- ALT or AST > 3X ULN and TBL > 1.5X ULN or INR > 1.5
- ALT or AST > 3X ULN with the appearance of fatigue, nausea, vomiting, right upper quadrant pain or tenderness, fever, rash, and/or eosinophilia (> 5%)
- ALT or AST > 5X ULN for more than 2 weeks
- ALT or AST >8X ULN

If liver chemistry tests meet any of the above criteria, repeat testing should be performed within 48 to 72 hours and the patient followed until resolution.

Patients meeting any of the following confirmed QT/QTc-related criteria must be withdrawn from the study by the Investigator:

- QTcF interval > 500 ms
- QTcF interval > 480 ms AND increase from Baseline ≥ 60 ms
- QTcF interval > 480 ms associated with syncope, life-threatening arrhythmias, resuscitated cardiac arrest, or seizure

The Investigator must also discontinue/withdraw a patient's participation in the study if any of the following criteria apply:

- Pregnancy
- Significant protocol violation/lack of compliance with the study and/or study procedures non-compliance with IP for discontinuation of patient is defined as < 50%.
- Severe constipation (e.g., obstipation with manual evacuation indicated) and/or severe, persistent, or worsening abdominal pain
- Any significant worsening on postdose C-SSRS indicative of active suicidal ideation with intent to act (defined as C-SSRS Suicidal Ideation category score of 4 or 5) or behavior (either preparatory acts/behavior, aborted attempt, interrupted attempt, or actual attempt)
- Severe depression or anxiety based on a HADS Depression or Anxiety score ≥ 15, or a QIDS-C Total Score ≥ 16.

• Any severe psychiatric or CNS AE as determined by the Investigator.

The Investigator may discontinue/withdraw a study patient's participation in the study if any of the following criteria apply:

Protocol RVT-1201-2002

Effective: 19JAN2022

• Behavioral or administrative reason

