APPENDIX 3. LIVER SAFETY: SUGGESTED ACTIONS AND FOLLOW-UP ASSESSMENTS

Protocol RVT-1201-2002

CTCAE Grade	Description	IP	Symptom/treatment
Mild = 1	AST or ALT > 1.5X ULN < 3X ULN	Continue as planned	No action taken
Moderate = 2	AST or ALT ≥ 3X ULN and < 5X ULN and no signs of severe liver damage	Reduce to one pill BID or interrupt treatment (to be decided by Investigator, based on individual risk assessment.)	Re-test ALT and AST, as well as ALP, TBL, and eosinophils within 48-72 hours, then at ~7 days, then at ~2 weeks, and assess for signs of severe liver damage: If AST and ALT < 3X ULN after 2 weeks, return to initial dose if reduced, restart at reduced dose if interrupted. Monitor labs (see above) every 2 weeks for at least 8 weeks. If AST and ALT ≥ 3X ULN after 2 weeks or anytime thereafter, permanently discontinue study medication.
Severe = 3	AST or ALT increase to ≥ 5X ULN and < 8X ULN and no signs of severe liver damage	Interrupt treatment	Re-test ALT and AST, as well as ALP, TBL, and eosinophils within 48-72 hours, then at ~7 days, then at ~2 weeks, and assess for signs of severe liver damage: • If AST and ALT < 3X ULN after 2 weeks, restart at reduced dose. Monitor labs (see above) every week for 4 weeks, then

Protocol RVT-1201-2002 Effective: 19JAN2022

CTCAE Grade	Description	IP	Symptom/treatment
			every 2 weeks for at least 8 weeks.
			• If AST and ALT ≥ 3X ULN after 2 weeks or anytime thereafter, permanently discontinue study medication.
Life-threatening = 4	AST or ALT increase to ≥ 8X ULN or signs of severe liver damage:	Permanently Discontinue	Patients showing these laboratory abnormalities need to be followed up
	-Increase of liver transaminases (ALT or AST ≥ 3X ULN)		closely
	and		
	Appearance of fatigue, nausea, vomiting, right upper abdominal quadrant pain or tenderness, fever, rash and/or eosinophilia (> 5%)		
	or		
	TBL > 1.5X ULN		
	or		
	INR > 1.5		

Abbreviations: ALP = alkaline phosphatase; ALT = alanine aminotransferase; AST = aspartate aminotransferase; BID = twice daily; CTCAE = Common Terminology Criteria for Adverse Events; INR = international normalized ratio; IP = investigational product; ULN = upper limit of normal

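### Appendix 3 gives no explicit permanent-stop instruction when only one liver enzyme is still at or above 3X ULN after two weeks; separately, Section 2.3 prints a laxer bilirubin limit than the governing rule

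*Protocol*

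**What the plan says.** **Appendix 3 (liver safety), two-week decision.** Either enzyme is enough to enter the Grade 2 row: "AST or ALT ≥ 3X ULN and < 5X ULN and no signs of severe liver damage". The Grade 3 row is also entered on either enzyme, from 5X to below 8X ULN. Grade 2 calls for reduction to one pill BID or interruption; Grade 3 calls for interruption. Both rows set retests at 48 to 72 hours, about 7 days and about 2 weeks, and then give two outcomes.

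- Resume, Grade 2: "If AST and ALT < 3X ULN after 2 weeks, return to initial dose if reduced, restart at reduced dose if interrupted".
- Resume, Grade 3: "If AST and ALT < 3X ULN after 2 weeks, restart at reduced dose".
- Stop, both rows: "If AST and ALT ≥ 3X ULN after 2 weeks or anytime thereafter, permanently discontinue study medication".

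**Combined bilirubin limit.** The risk table in Section 2.3 lists withdrawal at "ALT or AST > 3X ULN and TBL > 2X ULN", with INR above 1.5 as an alternative in brackets. The mandatory list in Section 8.1 has "ALT or AST > 3X ULN and TBL > 1.5X ULN or INR > 1.5". The permanent-discontinuation (Grade 4) row of Appendix 3 also uses 1.5X ULN for bilirubin.

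**Which text governs.** Section 4.4.1.2 states: "If at any time, the criteria as outlined in Section 8 are met, the IP must be permanently discontinued". For the open-label extension, Section 7.12 states: "All criteria for IP and study termination are the same as in the Main Study and can be found in Section 8".

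**The concern.** A decision rule that is entered on *either* enzyme should leave no patient without an outcome at the decision point. Here both exits are joined by *and*, so they are not complements. The negation of *both below 3X* is *at least one at or above 3X*, but the stop branch asks for *both at or above 3X*.

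Hepatic enzyme elevation is a named adverse event of special interest (Section 9.3.1), and Appendix 3 is where Section 4.4.1.2 sends sites for reduction, restart and discontinuation. On the literal text, a Grade 2 patient whose dose was reduced and who still has one enzyme at 4X ULN after two weeks can stay on the reduced dose, while a patient with both enzymes at 4X must stop permanently. Different sites could handle the same patient differently.

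The Section 2.3 figure is a plain inconsistency between current sections. Anyone taking the limit from the benefit/risk table gets a cut-off 0.5X ULN higher than the mandatory one.

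**Working it through.** No sample-size or alpha figure bears on this point. The check compares the texts and works through their logic.

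**Step 1. Appendix 3 branches, read literally.** Resume if AST < 3 and ALT < 3; stop if AST ≥ 3 and ALT ≥ 3 (multiples of ULN).

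| AST | ALT | As written | With *or* in the stop branch |
|---|---|---|---|
| < 3 | < 3 | resume | resume |
| ≥ 3 | ≥ 3 | stop | stop |
| ≥ 3 | < 3 | neither | stop |
| < 3 | ≥ 3 | neither | stop |

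As written, 1 state resumes, 1 stops and 2 have no branch. With *or*, 1 resumes, 3 stop and none is left over. Setting each enzyme to 2X, 4X and 6X ULN in turn gives nine combinations. As written, 1 resumes, 4 stop and 4 have no branch (2/4, 4/2, 2/6 and 6/2). With *or*, all nine fall in exactly one branch.

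**Step 2. What Section 8.1 picks up.** For one enzyme persisting beyond two weeks with no symptoms or eosinophilia and with normal bilirubin and INR:

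| Level of the one enzyme | Stop under Section 8.1? |
|---|---|
| 3X, 4X, 5X ULN | no |
| above 5X ULN for more than two weeks | yes |
| above 8X ULN | yes, whatever the duration |

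So 2/6 and 6/2 are caught by the duration rule, and 2/4 and 4/2 are not. The residual gap is one enzyme at 3X to 5X ULN with no other trigger.

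**Step 3. Bilirubin limit.** Take a transaminase of 3.5X ULN and INR 1.0, and vary bilirubin (X ULN).

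| Bilirubin | Section 2.3 (> 2) | Section 8.1 (> 1.5) |
|---|---|---|
| 1.4, 1.5 | no | no |
| 1.6, 1.8, 2.0 | no | withdraw |
| 2.1 | withdraw | withdraw |

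The texts disagree only above 1.5X and up to 2X ULN, and there Section 2.3 is always the laxer. With Section 2.3 set to 1.5X, the two agree at every value tested.

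**The case against.** **The gap patient is still managed.** This is largely right. One enzyme at 4X ULN still meets the Grade 2 entry condition, so reduction or interruption continues to apply. Resuming is barred because it needs both enzymes below 3X. Dose reductions are discussed with the Medical Monitor (Section 4.4.1), safety concerns go to the Sponsor to decide on continuing (Section 9), events of special interest are followed to resolution or stabilization (Section 9.3.4), and the investigator may withdraw a patient for a laboratory abnormality (Section 8.1). A reader might infer that such a patient has no instruction at all or may return to full dose; the documents do not support that. What is missing is the explicit instruction to stop permanently. One limit on this defence is that 300 mg BID in the extension is a single tablet BID without placebo (Section 7.9). For those patients, reduction to one pill BID lowers nothing and only interruption does.

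**The change adds a stopping rule.** If *or* was always intended, the edit is a clarification. On the literal text, it makes stopping mandatory for one enzyme at or above 3X ULN after two weeks, which Section 8.1 does not require. That stands as a cost and is counted under the fix.

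**Section 2.3 is only a summary.** This also stands. Sections 4.4.1.2 and 7.12 make Section 8 govern, so a site following the mandatory rule uses 1.5X ULN. A reader might infer a missing bilirubin safeguard, but there is none: the stricter limit is the operative one.

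**INR in Section 8.1.** A reader might also infer that the unbracketed line makes INR above 1.5 a withdrawal criterion on its own. The line stands in a list of liver chemistry criteria, Section 2.3 ties INR to raised transaminases, and Appendix 3 is equally unbracketed in the text available. The misreading would only cause extra withdrawals. It is not part of this point.

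**Conclusion.** The point holds as two wording faults of unequal weight.

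The main one is in an operative safety rule. The stop branch in the Grade 2 and Grade 3 rows of Appendix 3 is not the complement of the resume branch, which leaves two of four enzyme states unassigned. After allowing for Section 8.1, the persistent gap is one enzyme at 3X to 5X ULN with no bilirubin, INR, symptom or eosinophil trigger. This rests on reading *and* literally; the likely intent is *or*, which is why one word repairs it.

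The secondary one is the bilirubin figure in Section 2.3. It is wrong against the governing text, in the laxer direction, by 0.5X ULN. Its practical effect is small because Section 8 governs.

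Both should be corrected, but neither undermines the design. The documents give no frequency for either situation, and none is estimated here.

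**What to change.** - **Appendix 3, Grade 2 and Grade 3 rows:** in the stop branch, change *AST and ALT* to *AST or ALT*, keeping the 3X ULN level, the two-week point and the wording on later rises. Leave the resume branch as it is.
- **Section 2.3:** change the combined bilirubin limit from 2X to 1.5X ULN, or replace the liver list with a cross-reference to Section 8.1.
- **Optional, editorial:** bracket the bilirubin and INR alternatives in Section 8.1; align the GGT wording in Section 2.3 with exclusion criterion 23; use the same sign at 8X ULN in Section 8.1 and Appendix 3.

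**Cost.** The edits can go into a clarification or the next routine amendment, with any ethics submission this requires. Sample size and planned analyses do not change; SAP Table 14 already tabulates bilirubin at both 1.5X and 2X ULN. The one substantive cost is that a few patients with a single persistently raised enzyme may stop who would not under the literal text. If their PVR is then missing for tolerability, SAP Section 7.1.2.2 imputes the worst value in their arm. That can happen because Protocol Section 8.2.1 seeks a catheterization at discontinuation only after at least 12 weeks of treatment. It is not automatic: the same section keeps patients who agree to visits in follow-up to Week 24.

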3. OBJECTIVES AND ENDPOINTS

Objectives	Endpoints/Criteria for Evaluation
Primary	Primary
To evaluate the effect of rodatristat ethyl on the percent change from baseline of pulmonary vascular resistance (PVR), as measured by right heart catheterization (RHC) in patients with PAH	Percent change from baseline to 24 weeks of PVR between an active arm and the placebo arm
Secondary	Secondary
To evaluate the effect of rodatristat ethyl from baseline to Week 24 on the following: O WHO FC O 6MWD O N-terminal pro-Brain Natriuretic	To evaluate the effect of rodatristat ethyl from baseline to Week 24 on the following: O Change from baseline in WHO FC O Change from baseline in 6MWD O Change from baseline in NT-proBNP
(NT-proBNP)	
To evaluate the effect of rodatristat ethyl from baseline to Week 24 on the following:	To evaluate the effect of rodatristat ethyl from baseline to Week 24 on the following:
• Safety	• Safety
 To assess safety & tolerability of rodatristat ethyl in patients with PAH Additional Hemodynamics (cardiac index, mean pulmonary artery pressure [mPAP], mean right atrial pressure [mRAP], mixed venous oxygen saturation [SvO2], and pulmonary artery compliance [PAC]) Time to Clinical Worsening (TTCW) defined as the first occurrence of a composite end point of: 1. Death from any cause, 2. Hospitalization for worsening PAH (any hospitalization for worsening PAH, lung or heart and lung transplantation, atrial septostomy, or initiation of parenteral prostanoid therapy), 3. Disease progression defined as a decrease of more than 15% from baseline in the 6-minute walk distance (6MWD) combined with WHO FC III or IV symptoms at 2 consecutive visits separated by at least 14 days (adjudicated). 	 Change in safety parameters including AEs, vital signs, laboratory values, and electrocardiogram (ECG) assessments Additional Change from baseline in cardiac index, mPAP, mRAP, SvO2 at rest and PAC Change from baseline in TTCW Death from any cause Change from baseline in right atrial size & RV function (TAPSE, tricuspid annular systolic velocity, & RV fractional area change) Change from baseline in PAH-SYMPACT Change from baseline in REVEAL Lite 2.0 Score PK/PD Population PK parameters of rodatristat ethyl, active metabolite rodatristat, M15, and other metabolites
o Death from any cause	incuronics

Objectives	S	Endpoints/Criteria for Evaluation
0	Echocardiographic measures of right atrial size & RV function (tricuspid annular plane systolic excursion [TAPSE], tricuspid annular systolic velocity, and RV fractional area change)	O Change from baseline in 5-hydroxyindoleacetic acid (5-HIAA; plasma and spot urine concentration)
0	Pulmonary Arterial Hypertension- Symptoms and Impact Questionnaire (PAH-SYMPACT)	
0	Register to Evaluate Early and Long- Term PAH Disease Management (REVEAL) Lite 2 score	
PK/PI)	
0	To assess the PK of rodatristat ethyl and metabolites	
0	To assess the effect of rodatristat ethyl on plasma and urinary 5-HIAA	
Explorato	ry	Exploratory
	e the effect of rodatristat ethyl from Week 24 on the following:	To evaluate the effect of rodatristat ethyl from baseline to Week 24 on the following:
ActignTo evathe pla	o Clinical Improvement (TTCI) aphy aluate the effect of rodatristat ethyl on asma concentration of selexipag and 333679	A > 10% increase in 6MWD or 30 meters AND an improvement to or maintenance of WHO FC II symptomatology, in the absence of a deterioration in clinical condition or death during the 24 weeks of the Main Study
ACT-	555079	• Change from baseline in actual daily activity, (counts/minute) as determined by actigraphy:
		Light to vigorous activity/dayModerate to vigorous activity/day
		o Total movement/day
		o Best 6-minute walk effort
		Plasma selexipag and ACT-333679 trough concentration at baseline and Week 4

Protocol RVT-1201-2002 Effective: 19JAN2022

